## 1.1 Riociguat

Riociguat is the first of a new class of drugs, the soluble guanylate cyclase (sGC) stimulators that acts in the nitric oxide pathway and is being developed for the treatment of pulmonary hypertension (PH). Riociguat has a dual mode of action: it sensitizes sGC to the body's own

nitric oxide (NO) and can also increase sGC activity in the absence of NO, causing vasorelaxation, anti-proliferation and anti-fibrotic effects. Riociguat is approved for adults in over 40 countries for the treatment of PAH and chronic thromboembolic pulmonary hypertension (CTEPH). Recent data presented has demonstrated long-term (2-year) safety and tolerability data in adult patients with PAH and CTEPH ([Rubin et al., 2015](#), [Simonneau et al., 2014](#)).

## 1.2 Rationale of the study and risk-benefit assessment - amended

There is an unmet medical need for children with group 1 PAH. Riociguat would be a new class of drugs tested in this patient population, and may provide a safe and effective drug for this life-threatening disease, as seen in adults.

sGC is an important regulator in the cardiovascular system and is present in vascular cells and platelets. The endogenous activator of sGC is endothelial cell-derived NO, which acts in paracrine fashion. In smooth muscle cells and in platelets NO activates sGC, resulting in an increased intracellular cyclic guanosine monophosphate (cGMP) level which induces vasorelaxation, and inhibition of cell proliferation and fibrotic effects. By increasing the sGC activity in the absence of NO, riociguat causes vasorelaxation, anti-proliferation and anti-fibrotic effects.

PATENT-1 was the pivotal study that led to the approval of riociguat (Adempas) for adults with PAH. The PATENT-1 study was a phase 3, double-blind study where 443 adult subjects with symptomatic PAH were randomly assigned to treatment and actually received placebo, riociguat in individually adjusted doses of up to 2.5 mg three times daily (2.5 mg–maximum group), or riociguat in individually adjusted doses that were capped at 1.5 mg three times daily (1.5 mg–maximum group). The 1.5 mg–maximum group was included for exploratory purposes, and the data from that group were analyzed descriptively. Subjects who were receiving no other treatment for pulmonary arterial hypertension and subjects who were receiving endothelin-receptor antagonists or (non-intravenous) prostanoids were eligible. The primary end point was the change from baseline to the end of week 12 in the distance walked in 6 minutes. Secondary endpoints included the change in pulmonary vascular resistance, N-terminal pro-brain natriuretic peptide (NT-proBNP) levels, World Health Organization (WHO) functional class, and time to clinical worsening, score on the Borg dyspnea scale, quality-of-life variables, and safety. By week 12, the 6-minute walk distance had increased by a mean of 30 m in the 2.5 mg–maximum group and had decreased by a mean of 6 m in the placebo group (least-squares mean difference, 36 m; 95% confidence interval, 20 to 52;  $P < 0.001$ ). Important for this current study, prespecified subgroup analyses showed that riociguat improved the 6-minute walk distance both in subjects who were receiving no other treatment for the disease AND in those who were receiving endothelin-receptor antagonists or prostanoids. There were significant improvements in pulmonary vascular resistance ( $P < 0.001$ ), NT-proBNP levels ( $P < 0.001$ ), WHO functional class ( $P = 0.003$ ), time to clinical worsening ( $P = 0.005$ ), and Borg dyspnea score ( $P = 0.002$ ). The most common serious adverse event in the placebo group and the 2.5 mg–maximum group was syncope (4% and 1%, respectively). In conclusion, riociguat significantly improved exercise capacity and secondary efficacy end points in subjects with pulmonary arterial hypertension ([Ghofrani et al., 2013](#)). In PATENT-1, riociguat improved the 6-minute walk distance in both patients who were receiving no therapy for the disease and patients who were receiving endothelin-receptor antagonists or prostanoids.

Further details can be found in the latest available version of the investigator's brochure, which contains comprehensive information on the study drug.

Based on the positive results of riociguat in adult subjects with PAH, children with PAH may also benefit from treatment with riociguat, e.g. those pre-treated with bosentan.

As previously discussed, Revatio (INN: sildenafil) is approved in Europe and has now become standard of care. Riociguat and PDE5 inhibitors such as sildenafil act on the NO-sGC-cGMP signaling pathway. Thus, an additive effect on pulmonary and systemic circulation may be expected. Non-clinical studies in animal models showed an additive systemic blood pressure lowering effect when riociguat was combined with either sildenafil or vardenafil. With increased doses, more than additive effects on systemic blood pressure were observed in some cases. The interaction of riociguat and PDE5i was investigated in a clinical study (PATENT-Plus; study 15096). PATENT-Plus was designed as an interaction study to evaluate changes in blood pressure following 1, 1.5, 2, and 2.5 mg riociguat TID (i.e., the IDT regimen) compared to placebo treatment on the background of stable sildenafil pre-treatment in subjects with symptomatic PAH.

On the basis of the safety, tolerability and efficacy data available, and in particular the apparent high rate of discontinuations due to hypotension and a lack of overall clinical benefit in the patient population studied, a positive benefit risk assessment could not be established and therefore riociguat should not be used in combination with sildenafil. After a review of the above data, the long-term extension phase of Patent-Plus was discontinued. Based on these considerations and in agreement with the CHMP (Committee for Medicinal Products for Human Use) (Adempas\_EMEAHC2737) riociguat on top of sildenafil (Revatio in Europe) is contraindicated in the EU-SmPC. Accordingly, use of PDE5 inhibitors is a key exclusion criterion in this current study.

In general, treatment with riociguat is expected to cause comparable mode of action related side effects in children and adolescents as in adults. In growing rats, morphological changes (widening of the growth plates, increase of bone mass) of the bones have been found as additional adverse effects related to mode of action. Although the regulation of bone homeostasis via the NO-sGC-cGMP-PKG pathway holds true for all species including humans, the effect of sGC stimulation on the growing bone is yet unclear. Considering the severity and prognosis of PAH and the fact that the bone findings in rats were seen at 3-4 fold of human exposure, and that the findings were reversible and can be monitored in the clinical setting, the preclinical bone findings are considered as not prohibitive for the initiation of a clinical study in children.

The protocol was developed in accordance with ICH Good Clinical Practice, and other ICH/EMA guidelines for conducting clinical trials in pediatric population, in particular the ICH Topic E 11 (Clinical Investigation of Medicinal Products in the Pediatric Population) and the guideline on Ethical Considerations for Clinical Trials on Medicinal Products Conducted with the Pediatric Population.

The necessity of minimizing any possible burden and any potential risk for participating child and adolescent patients was taken into consideration and addressed during the development of this protocol. In order to provide guidance for investigators this protocol describes use of all study procedures, as well as outlines any potential related burden for participating patients, whenever applicable, in the respective chapters. In terms of the IMD administration the titration phase has been implemented (as described in the Section 5.1.1 "Body-weight

adjusted individual dose titration regimen”), as well as a dosing pipette for administration of oral suspension will be used. Educational material for training on the dosing pipette use and dose administration for study site staff, as well as for the patients and their caregivers, to ensure adequate dosing pipette use and treatment compliance will be distributed.

The study design includes standard procedures for pediatric PAH management, and only a few additional, study specific procedures have been included wherever absolutely necessary to ensure the study conduct, and monitoring of safety of enrolled patients. Study-specific procedures are: ECGs, Echocardiogram, urine or serum pregnancy testing for female patients of childbearing potential, selected blood sampling, and the left-hand X-ray for monitoring of bone growth. The above listed study specific procedures are non-invasive, standard medical care procedures. Laboratory samples will be restricted to the selected laboratory tests at screening (only if historical data is not available), visit 1, 5 and 9. Pharmacokinetic samples and blood sampling for study purposes will be aligned with clinically required blood tests whenever possible in order to avoid additional burden of a painful procedure and blood volume taken (see the subchapter “Laboratory parameters” in Section 6.2). Blood samples for pharmacokinetic analysis will have the blood volume minimized to 1 ml per sample. All blood samples collection will be performed by pediatric specialist staff and will be performed with the use of techniques like distraction and local anesthetic techniques, if applicable, to reduce the burden for patients. The left hand X-ray for monitoring of bone growth will be performed and assessed according to the established method. The rare periodicity of this X-ray examination, as well as the standard precautions will ensure minimal and therefore acceptable exposure to radiation (Section 6.2 Safety outcomes).

Investigators are mandated and trained to report adverse events, and all the respective definitions, criteria for qualifying AEs, and their reporting, as well as a description of pharmacovigilance procedures are included in a separate section of this protocol (Section 8.8). The monitoring of safety of participating patients by investigators and the sponsor is ensured by adherence to pharmacovigilance regulations and implementation of study specific monitoring measures (e.g. observation and evaluation of potential AEs of special interest, patients’ growth and bone growth monitoring). Close monitoring and ongoing medical review will be performed by the sponsor. An independent Data Monitoring Committee (DMC, which will be acting according to a DMC Charter) will meet periodically to review the safety data of enrolled patients, as well as the scientific merit of the trial. In addition a Steering Committee (SC) will ensure a scientifically sound and safe conduct of the study. Both, the DMC and the SC, are described in a separate subsection of this protocol (6.6 Study committees”).

The expected benefit-risk balance of riociguat is considered positive if used in adherence to this clinical trial protocol and in accordance with the recommendations and guidance given in the Investigator’s Brochure.

*(Note: The section was widened according to Amendment 3, to better describe the minimization of burden degree of pediatric subjects, see Sections 17.1.1.5 and 17.1.1.16. The section was modified according to Amendment 6, see Section 17.3.1.8.)*

## 2. Study objectives - amended

The primary objectives:

- To evaluate safety, tolerability and pharmacokinetics of oral riociguat treatment

Secondary objectives:

- Exploratory efficacy. To characterize the pharmacodynamic profile of riociguat comprising the following exploratory parameters: time to clinical worsening (TTCW), exercise capacity (6MWD test), functional capacity (measured by WHO FC), laboratory biomarkers (NT-proBNP or BNP), Quality of Life (QoL) measurements (SF-10, PedsQL), echocardiographic variables

Other objective is:

- To assess taste and texture of the pediatric formulation(s) by use of a questionnaire

*(Note: The text was modified according to Amendment 3, see Section 17.1.1.3. The text was modified according to Amendment 5, see Section 17.2.1.7. The section was modified according to Amendment 6, see Sections 17.3.1.2 and 17.3.1.6.)*

## 3. Study design

This is an international, multicenter, single-arm, open-label study to evaluate the safety, tolerability and pharmacokinetics of a body-weight adjusted riociguat regimen in subjects aged between  $\geq 6$  years old and  $< 18$  years old who have been diagnosed with idiopathic PAH, hereditary PAH, or PAH associated with connective tissue disease or congenital heart disease with shunt closure. These subjects must be on stable treatment with PAH medications (ERA and/or PCA) prior to receiving the first dose of riociguat (EMA, 2009, EMA, 2012a, eMC, 2015a, eMC, 2015b).

*(Note: The Section was modified according to Amendment 6, see Section 17.3.1.2.)*

### 3.1 Study description - amended

After providing written informed consent and assent (if applicable) subjects will undergo a screening evaluation to determine their eligibility. Eligible subjects – once on stable background treatment with PAH medications (ERA and/or PCA) - will start body-weight adjusted individual dose titration (IDT) regimen as described in section 5.1.1. After the individual titration phase of maximum of 8 weeks, subjects will enter the 16-week maintenance phase. The last dose administered at Visit 4 will be regarded as individual optimal dose and subject will receive that treatment during the maintenance phase.

Subjects of the older age cohort ( $\geq 12$  to  $< 18$  years) will be treated first. After 5 patients of this age cohort have reached their optimal dose and received this dose until assessment of their first control x-ray of left hand at week 24, an independent Data Monitoring Committee (DMC) will give recommendations to the Steering Committee (SC) whether to continue with enrolment in this age cohort and open enrollment in the subsequent lower age cohort ( $\geq 6$  to  $< 12$  years).

Children who require treatment with riociguat for more than 24 weeks will be offered participation in an extension study and continuation until market approval of riociguat for the

pediatric population or until they are 18 years of age (whatever comes first). Subjects reaching adulthood can be transitioned to commercially-available Adempas.

The primary objective is the evaluation of safety and tolerability as well as the pharmacokinetic properties of riociguat in the pediatric population. The DMC will monitor the subjects' safety on an ongoing basis and give recommendations to the SC.

For all subjects, visits are scheduled at regular time points (see [Table 0-1](#)). Subjects who prematurely discontinue study drug or do not consent to participate in the long-term extension phase will be seen at the safety follow-up visit. During all contacts, the treatment and clinical course of the subject will be evaluated. Subjects with suspected safety concerns (for safety outcomes see section [6.2](#)) will undergo confirmatory testing as per standard of care. Blood samples for PK will be taken at defined time points (see [Table 0-2](#)).

The reason why subjects did not pass the screen of in- and exclusion criteria after obtaining informed consent/child assent will be documented.

### **Primary completion**

The primary completion event for this study is when the last visit of the last subject for all centers has occurred after 24 weeks of treatment.

### **End of study**

The end of the study will be reached as soon as the last visit of the last subject has been reached in all centers in all participating countries (EU and non-EU).

A clinical study report (CSR) will be written after the primary completion. A separate CSR will be prepared after completion of the optional long-term extension (LTE).

*(Note: The wording in Primary completion and in End of the study was modified according to Amendment 3, see Section 17.1.1.2. The Section was modified according to Amendment 6, see Section 17.3.1.2. The wording in End of the study was modified according to Amendment 14, see Section 17.6.)*

## 4. Study population

### 4.1 Planned number of subjects - amended

Children on treatment with ERAs and/or PCAs can be enrolled. At least 20 children on treatment with bosentan or other Endothelin Receptor Antagonists (ERA) must be enrolled in the study.

The sponsor commits to put efforts in enrolling equal number of subjects in each of the  $\geq 12$  to  $< 18$  year and the  $\geq 6$  to  $< 12$  year age cohort overall. Enrolment will be started with children from 12 to less than 18 years of age.

After 5 patients in the  $\geq 12$  to  $< 18$  years old group have reached their optimal dose, have been treated on their maintenance dose and obtained the control x-ray of left hand at week 24, their data will be evaluated by DMC. Only after obtaining positive safety and efficacy data in the first 5 patients, enrolment in the group from 6 to less than 12 years of age will be started.

The sponsor will make every effort to facilitate an equal distribution between the two age cohorts with a minimum of 5 patients in each age cohort. In case of inadequate availability of patients in the age group  $\geq 6$  to  $< 12$  years total enrolment will be stopped only if at least 5 patients of this younger age group have been enrolled.

*(Note: The Section was modified according to Amendment 6, see Section 17.3.1.2. The Section was modified according to Amendment 9, see Section 17.4.1.9)*

### 4.2 Inclusion criteria – amended

1. Children from 6 years to less than 18 years of age with pulmonary arterial hypertension (PAH)
2. Diagnosed with PAH :
  - Idiopathic (IPAH)
  - Hereditary (HPAH)
  - PAH associated with (APAH)
    - Connective tissue disease
    - Congenital heart disease with shunt closure more than 6 months ago (no open shunts, confirmed by RHC no less than 4 months after surgery)

Regardless of the type of PAH, the following findings are not exclusionary:

- Patent foramen ovale (PFO) and asymptomatic, isolated, ostium secundum atrial septal defect (OS-ASD)  $\leq 1$  cm (both confirmed by echocardiogram) and not associated with hemodynamic alterations indicative of significant shunt, e.g. Qp/Qs ratio less  $< 1.5:1$  are not exclusionary
3. Pulmonary arterial hypertension (PAH), diagnosed by right heart catheterization (RHC) at any time prior to enrolment (for patients with closed shunts – RHC no less than 4 months after surgery)
  4. Pulmonary arterial hypertension confirmed by a RHC at any time prior to start of study, with mean pulmonary artery pressure (PAPmean)  $\geq 25$  mmHg at rest, pulmonary capillary

wedge pressure (PCWP) or left ventricular end-diastolic pressure (LVEDP)  $\leq 15$  mmHg, and pulmonary vascular resistance (PVR)  $> 240$  dyn $\cdot$ sec $\cdot$ cm $^{-5}$  (i.e.,  $\geq 3.0$  wood units $\cdot$ m $^2$ )

5. Patients must be on standard of care PAH medications, allowing Endothelin Receptor Antagonists (ERA) and/or Prostacyclin Analogues (PCA), for at least 12 weeks prior to baseline visit.

Two groups of patients will be included:

- Prevalent: Patients currently on PAH medication (allowing ERA and/or PCA) who need additional treatment (discretion of the investigator)
- Incident: Treatment naïve patients initiated on PAH medication (allowing ERA and/or PCA) and then riociguat added once patients are stable on standard of care

6. WHO functional class I-III

7. Adolescent females of childbearing potential can only be included in the study if a pregnancy test is negative. Adolescent females of childbearing potential must agree to receive sexual counseling and use effective contraception as applicable. ‘Effective contraception’ is defined as progestogen-only hormonal contraception associated with inhibition of ovulation (implant), intrauterine device (IUD), intrauterine hormone-releasing system (IUS), or any combination of adequate methods of birth control (e.g. condoms with hormonal contraception). Agreement to use contraception is required from the signing of the informed consent form up until 4 weeks after the last study drug administration.

8. Young men must agree to use adequate contraception when sexually active.

9. Written informed consent provided and if applicable child assent provided

*(Note: The text was modified according to Amendment 3, please see Section 17.1.1.16. The Section was modified according to Amendment 6, see Section 17.3.1.2. The Section was modified according to Amendment 9, see Section 17.4.1.1, 17.4.1.2, and 17.4.1.3)*

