### **6.1.1 Pre-treatment phase (Visit 0, Day -14 to -1) - amended**

The parents/legal guardians and children will be given an explanation about the study and will be given sufficient time to consider their participation in the study and to ask any questions. Afterwards, informed consent and, if applicable, assent will be obtained (see section 11.2). Collection of AEs starts after informed consent is signed. If the subject passes the screen of inclusion and exclusion criteria, the subject will be eligible to enter the study. The following procedures will be performed if no historical data (not older than 30 days) are available:

- Obtain demographics (incl. smoking status) and medical history
- Record concomitant PAH specific medication
- Perform physical examination (incl. height, weight, vital signs and pubertal assessment using Tanner scale [see section 18.3])
- Obtain blood sample if AST, ALT, creatinine, blood urea nitrogen (BUN), gamma-glutamyltransferase (GGT), uric acid (UA), total bilirubin (T-Bil), Albumin (Alb), Sodium (Na), potassium (K), Calcium (Ca), P and complete blood count (CBC) are not available within 30 days prior to screening visit
- Perform ECG (electrocardiogram)
- Pregnancy test for females of childbearing potential
- Child Health Questionnaire (SF-10 and PedsQL Generic Core Scales self-report) (section 18.2 and 18.7)
- In case RHC has been performed for a study subject before enrollment, record the most recent RHC parameters to the eCRF (timing of RHC not limited to the period of Day -14 to -1)

*(Note: The text was modified according to Amendment 3, see Sections 17.1.1.8 and 17.1.1.16. The Section was modified according to Amendment 5, see Sections 17.2.1.1 and 17.2.1.2. The Section was modified according to Amendment 6, see Sections 17.3.1.2 and 17.3.1.3. The Section was modified according to Amendment 9, see Section 17.4.1.8.)*

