20 JUL 2020

Version 7.0

Page: 187 of 211

	exposure, and should be used with caution.	increase in exposure when riociguat was administered on top of Triumeq®. In vitro investigations identified abacavir as CYP1A1 inhibitor reducing riociguat clearance.
5.4 Formulation and dose Table 5-2	To correct the volume of 7.0 mL to 7.5 mL for the body weight category of $\geq 35$ <40 kg on 2.0 mg equivalent dose	The correct volume of suspension to administer 1.12 mg is 7.5 mL.
5.4 Formulation and dose Table 5-2	Dosing recommendation for patients with body weight $\geq 12$ <14 kg added	Dosing recommendation required for children with body weight <14 kg. According to in-/exclusion criteria patients with <14 kg may be enrolled.  With the minimum age criteria of 6 years BW < 12 kg otherwise matching all other eligibility criteria is not expected. With the given formulations and dosing devices dosing of patients <12 kg is not feasible.
6.1.6 Optional long-term extension phase	Pregnancy testing is to be performed in 4-weekly intervals starting at Visit 1 until 4 weeks after the patient stops intake of study drug	Frequency of pregnancy tests requested by HA
6.1.6 Optional long-term extension phase	To clarify the conditions for transitioning into the optional LTE phase.	Transition must have time frame - especially for subject who becomes 18 years old in main study phase in order to allow them to enter the LTE
6.1.6 Optional long-term extension phase	Clarified that 6MWD test and echocardiography can be performed at every second visit in LTE at the discretion of the investigator	Clarification
6.1.6 Optional long-term extension phase	Child Health-related Questionnaire (SF-10) and PedsQ: The age version used must match with subject's actual age at time of completing the questionnaire.	Clarification
6.4 Pharmacokinetics – amended	Name of the peak sample is changed to post-dose sample	Samples are taken after dosing and not exactly at peak plasma concentrations, therefore the name of PK sampling was clarified
6.5 Study guidelines for parents and children	To explicitly describe one investigator task at visits: to check the patient's home SBP monitoring form.	For completeness

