6.1.1 Inclusion-/Exclusion criteria

Data from the assessment of inclusion and exclusion criteria will be presented in listings for all subjects who signed informed consent/assent and failed the inclusion/exclusion criteria.

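### Inclusion criterion 4 equates an unindexed PVR limit with a body-surface-indexed one; the two agree only at a body surface area of 1.0 m²

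*Protocol*

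**What the plan says.** Criterion 4 of Protocol Section 4.2 combines limits on mean pulmonary artery pressure (at least 25 mmHg), wedge or left ventricular end-diastolic pressure (at most 15 mmHg) and resistance. The resistance part reads "pulmonary vascular resistance (PVR) $> 240$ dyn $\cdot$ sec $\cdot$ cm $^{-5}$ (i.e., $\geq 3.0$ wood units $\cdot$ m $^2": one figure, followed by a second in brackets. The wording joining them presents the second as the first in other units.

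The criterion applies to a wide range of body sizes. Criterion 1 admits "Children from 6 years to less than 18 years of age with pulmonary arterial hypertension (PAH", and Table 5-2 in Section 5.4 gives doses from the band starting at 12 kg up to 50 kg and over.

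The date of the qualifying catheterisation is open: "Pulmonary arterial hypertension confirmed by a RHC at any time prior to start of study". At screening, Section 6.1.1 has sites "record the most recent RHC parameters to the eCRF (timing of RHC not limited to the period of Day -14 to -1".

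In the SAP, Section 6.1.1 has eligibility data "presented in listings for all subjects who signed informed consent/assent and failed the inclusion/exclusion criteria". Section 6.4.4 lists the BSA measured at screening without linking it to resistance. Neither document gives a conversion or a rule for choosing between the two limits. The amendment text reproduced for Section 4.2 (Amendments 3, 6 and 9) and the Amendment 12 summary show no change to the resistance limit.

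**The concern.** The unit dyn·s·cm⁻⁵ measures resistance as such. The unit WU·m² measures resistance multiplied by BSA. A fixed cut-off on one scale is a cut-off that moves with body size on the other, so the two cannot be one threshold in a population aged 6 to under 18.

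What is at stake is whether a given child is eligible. Two sites could apply the same sentence to the same catheter data and decide differently, and the direction of disagreement would follow body size. Whether such a child counts as a protocol deviation cannot be decided from the text. The signs also differ (strict in one form, non-strict in the other), but that matters only for a value exactly at the limit.

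**Working it through.** **Inputs.** From criterion 4: 240 dyn·s·cm⁻⁵, 3.0 WU·m² and the two pressure limits. The BSA range of 0.7 to 1.7 m² and the cardiac indices in the cases below are assumptions; the documents give no resistance or BSA data.

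**Step 1: the plan's own figure.** One Wood unit is 1 mmHg·min/L, so 1 WU = 1333.22 / (1000/60) = 79.99 dyn·s·cm⁻⁵. Then 240 / 79.99 = 3.00 WU. The number 3.0 reproduces for plain Wood units. It would also reproduce if both figures were indexed (240 dyn·s·cm⁻⁵·m² = 3.0 WU·m²). It does not reproduce for the printed mixture.

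**Step 2: the two limits across BSA.** Indexed resistance = resistance × BSA. The first limit in indexed units is therefore 3.00 × BSA, and the second in unindexed units is (3.0 / BSA) × 79.99.

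| BSA (m²) | 240 dyn·s·cm⁻⁵ in WU·m² | 3.0 WU·m² in dyn·s·cm⁻⁵ |
|---|---|---|
| 0.7 | 2.1 | 343 |
| 0.8 | 2.4 | 300 |
| 1.0 | 3.0 | 240 |
| 1.2 | 3.6 | 200 |
| 1.5 | 4.5 | 160 |
| 1.7 | 5.1 | 141 |

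The gap runs from 343/240 = 1.43 (+43%) to 141/240 = 0.59 (−41%).

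**Step 3: where the limits disagree.** At BSA 0.7, resistance between 240 and 343 dyn·s·cm⁻⁵ meets only the first limit. At 1.5, 160 to 240 meets only the second; at 1.7, 141 to 240. Outside these bands the limits agree: at BSA 0.7, 500 dyn·s·cm⁻⁵ is 6.25 × 0.7 = 4.4 WU·m² and meets both.

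**Step 4: two illustrative children who satisfy the pressure limits.** Resistance = (mean pulmonary artery pressure − wedge pressure) / (cardiac index × BSA).

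- (a) Pressures 25 and 13, cardiac index 4.5, BSA 0.7: 12 / 3.15 = 3.81 WU = 305 dyn·s·cm⁻⁵; indexed, 12 / 4.5 = 2.67 WU·m². Meets the first limit only.
- (b) Pressures 35 and 15, cardiac index 4.0, BSA 1.7: 20 / 6.8 = 2.94 WU = 235 dyn·s·cm⁻⁵; indexed, 20 / 4.0 = 5.0 WU·m². Meets the second limit only.

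**Step 5: can it be checked afterwards?** Only with BSA at the date of catheterisation. Suppose a catheterisation at BSA 0.7 gave 260 dyn·s·cm⁻⁵, which is 3.25 WU or 3.25 × 0.7 = 2.28 WU·m². Indexed with a later screening BSA of 1.0 it would read 3.25 WU·m² (+43%) and would wrongly appear to meet the second limit.

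**The case against.** The strongest reply is that the criterion names one quantity with one operative limit and that the bracket is only a gloss. Because 240/80 is exactly 3.0 and the abbreviation list defines PVR but no indexed form, the m² may simply be stray. That reading is plausible, but the documents do not settle it: the dyn figure could equally have been meant as indexed.

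Second, the consequence is small. The study is single-arm and descriptive, has no formal sample-size calculation, and analyses every assigned child who takes a dose. No estimate depends on the limit. This stands.

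Third, other outputs touch the same ground. SAP Section 6.2.3 tabulates catheter parameters where available, and Section 4.6 lists all protocol deviations. These describe part of the haemodynamics, but neither shows which limit a child was enrolled under.

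Fourth, the illustrative cases sit near the edges of the criterion and rest on assumed inputs. They show that disagreement is possible, not that it is common. This also stands.

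Finally, the documents do not say whether enrolment is still open. If it has closed, rewording changes no eligibility decision, and only the count of discordant children keeps practical value.

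**Conclusion.** The concern holds. As written, criterion 4 contains two different thresholds presented as one, and they agree only at BSA 1.0 m². That result follows from the units alone and needs no assumption.

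The size of the gap (+43% to −41% of 240 dyn·s·cm⁻⁵) rests on the assumed BSA of 0.7 to 1.7 m². It measures the distance between cut-offs, not a number of children. No enrolled child is shown to be affected. Because this is an eligibility threshold and not a labelling detail, it should be corrected, although no planned analysis would change.

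**What to change.** 1. **Reword criterion 4.** State which limit governs, in one unit system with one inequality sign, and drop the claimed equivalence. The choice of threshold is the sponsor's. The cost is a wording change to one criterion.

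2. **Report discordance where possible.** Where the recorded catheterisation is the qualifying one, and its data include resistance plus BSA (or indexed resistance) at that date, report how many enrolled children meet only one limit. Report the rest as not assessable. Do not index an older catheterisation with screening BSA. The documents do not list which catheter parameters are recorded, so some children may need a return to source records.
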